11.3. Participant Replacement

Participants who fail to complete the Visit 4 (Day 25) and Visit 5 (Day 26) photosensitivity and biopsy assessments may be replaced according to the following rules, which depend on the reason for withdrawal from the study:

- No more than three individuals withdrawn for reasons due to concerns over safety or tolerability of tofacitinib may be replaced.
- No more than 18 individuals withdrawn for reasons other than safety or tolerability concerns, including “external” reasons unrelated to the individual (e.g., study site closed due to COVID-19), may be replaced.

11.4. Follow-up after Early Study Withdrawal

Participants who withdraw from the study for any reason will be asked to consent to a final Early Termination Visit to complete clinical and safety assessments. See Protocol Section 8.4 *Early Termination Visits* for more information.

11.5. Study Stopping Rules

There are no pre-specified study stopping rules.

If any of the events described in Section 12.8.2.2, *Ad hoc DSMB Reviews* occur, an ad hoc DSMB review will occur. After review of the data, the Data Safety Monitoring Board (DSMB) will make recommendations regarding the study conduct and/or continuation.

12. Safety Monitoring and Reporting

12.1. Overview

This section defines the types of safety data that will be collected under this protocol and outlines the procedures for appropriately collecting, grading, recording, and reporting those data. Adverse events that are classified as serious according to the definition of health authorities must be reported promptly (per Section 12.5, *Reporting of Serious Adverse Events and Adverse Events*) to the sponsor, DAIT/NIAID. Appropriate notifications will also be made to site principal investigators, Institutional Review Boards (IRBs).

Information in this section complies with International Council for Harmonization (ICH) Guideline E2A: Clinical Safety Data Management: Definitions and Standards for Expedited Reporting, ICH Guideline E-6: Guideline for Good Clinical Practice, the principles of 21CFR Parts 312 and 320, and applies the standards set forth in the National Cancer Institute (NCI), Common Terminology Criteria for Adverse Events (CTCAE), Version 5.0 : [Common Terminology Criteria for Adverse Events PDF](#).

12.2. Definitions

12.2.1. Adverse Event (AE)

Any untoward or unfavorable medical occurrence associated with the subject’s participation in the research, whether or not considered related to the subject’s participation in the research (modified from the definition of adverse events in the 1996 International Conference on Harmonization E-6 Guidelines for Good Clinical Practice) (from OHRP

"Guidance on Reviewing and Reporting Unanticipated Problems Involving Risks to Subjects or Others and Adverse Events (1/15/07)" <http://www.hhs.gov/ohrp/policy/addevntguid.html#Q2>)

12.2.2. Suspected Adverse Reaction

Any adverse event for which there is a reasonable possibility that the investigational drug [or investigational study therapy regimen] caused the adverse event. For the purposes of safety reporting, 'reasonable possibility' means there is evidence to suggest a causal relationship between the drug and the adverse event. A suspected adverse reaction (SAR) implies a lesser degree of certainty about causality than adverse reaction, which means any adverse event caused by a drug (21 CFR 312.32(a)).

For this study, a SAR will include any untoward or unfavorable medical occurrence associated with:

- Study therapy: tofacitinib
- Skin biopsy
- UVB exposure

12.2.3. Unexpected Adverse Event

An adverse event or suspected adverse reaction is considered "unexpected" if it is not listed in the package insert or is not listed at the specificity, severity or rate of occurrence that has been observed; or is not consistent with the risk information described in the general investigational plan or elsewhere in the Investigational New Drug (IND).

12.2.4. Serious Adverse Event

An adverse event or SAR is considered "serious" if, in the view of either the investigator or DAIT/NIAID, it results in any of the following outcomes (21 CFR 312.32(a)):

1. Death.
2. A life-threatening event: An AE or SAR is considered "life-threatening" if, in the view of either the investigator or DAIT/NIAID, its occurrence places the participant at immediate risk of death. It does not include an AE or SAR that, had it occurred in a more severe form, might have caused death.
3. Inpatient hospitalization or prolongation of existing hospitalization.
4. Persistent or significant incapacity or substantial disruption of the ability to conduct normal life functions.
5. Congenital anomaly or birth defect.
6. Important medical events that may not result in death, be life threatening, or require hospitalization may be considered serious when, based upon appropriate medical judgment, they may jeopardize the participant and may require medical or surgical intervention to prevent one of the outcomes listed above.

Elective hospitalizations or hospital admissions for the purpose of conduct of protocol mandated procedures are not to be reported as an SAE unless hospitalization is prolonged due to complications.

12.3. Grading and Attribution of Adverse Events

12.3.1. Grading Criteria

The study site will grade the severity of adverse events experienced by the study participants according to the criteria set forth in the National Cancer Institute's Common Terminology Criteria for Adverse Events (CTCAE) 5.0. This document (referred to herein as the NCI-CTCAE manual) provides a common language to describe levels of severity, to

analyze and interpret data, and to articulate the clinical significance of all adverse events. The NCI-CTCAE has been reviewed by the Protocol Chair and has been deemed appropriate for the population to be studied in this protocol.

Adverse events will be graded on a scale from 1 to 5 according to the following standards in the NCI-CTCAE manual:

- Grade 1 = mild adverse event.
- Grade 2 = moderate adverse event.
- Grade 3 = severe or medically significant.
- Grade 4 = life-threatening consequences; urgent intervention indicated.
- Grade 5 = death.

Events of Grade 2 or higher and all Grade 1 or higher COVID-19 events will be recorded on the appropriate AE eCRF for this study according to 12.4, *Collection and Recording of Adverse Events*.

For grading an abnormal value or result of a clinical or laboratory evaluation (including, but not limited to, a radiograph, an ultrasound, an electrocardiogram etc.), a treatment-emergent adverse event is defined as an increase in grade from the last assessment prior to a participant starting treatment, or from the last post-baseline value that doesn't meet grading criteria. Changes in grade from screening to Day 0, Day 1, and treatment initiation (Day 2) will also be recorded as adverse events, but are not treatment-emergent. If a specific event or result from a given clinical or laboratory evaluation is not included in the NCI-CTCAE manual, then an abnormal result would be considered an adverse event if changes in therapy or monitoring are implemented as a result of the event/result.

Liver function abnormalities will be graded using criteria from NCI-CTCAE version 4.0, defined relative to the ULN as follows:

- Aspartate aminotransferase [AST] increased
 - Grade 1: > ULN – 3.0x ULN
 - Grade 2: > 3.0x ULN - 5.0x ULN
 - Grade 3: > 5.0x ULN - 20.0x ULN
 - Grade 4: > 20.0x ULN
- Alanine aminotransferase [ALT] increased
 - Grade 1: > ULN – 3.0x ULN
 - Grade 2: > 3.0x ULN - 5.0x ULN
 - Grade 3: > 5.0x ULN - 20.0x ULN
 - Grade 4: > 20.0x ULN
- Alkaline phosphatase [ALP] increased
 - Grade 1: > ULN – 2.5x ULN
 - Grade 2: > 2.5x ULN - 5.0x ULN
 - Grade 3: > 5.0x ULN - 20.0x ULN
 - Grade 4: > 20.0x ULN
- Blood bilirubin increased
 - Grade 1: > ULN – 1.5x ULN
 - Grade 2: > 1.5x ULN - 3.0x ULN
 - Grade 3: > 3.0x ULN - 10.0x ULN
 - Grade 4: > 10.0x ULN

12.3.2. Attribution Definitions

The relationship, or attribution, of an adverse event to the study therapy regimen or study procedure(s) will initially be determined by the site investigator and recorded on the appropriate AE/SAE eCRF. Final determination of attribution for safety reporting will be determined by DAIT/NIAID. The relationship of an adverse event to study therapy regimen or procedures will be determined using the descriptors and definitions provided in Table 12.1.

For additional information and a printable version of the NCI-CTCAE manual, consult the NCI-CTCAE web site:
<http://ctep.cancer.gov/reporting/ctc.html>.

Table 12.1 Attribution of Adverse Events

Code	Descriptor	Relationship (to primary investigational product and/or other concurrent mandated study therapy or study procedure)
Unrelated Category		
1	Not Related	The adverse event is clearly not related: there is insufficient evidence to suggest a causal relationship.
Related Categories		
2	Possibly Related	The adverse event has a reasonable possibility to be related; there is evidence to suggest a causal relationship.
3	Related	The adverse event is clearly related.

12.4. Collection and Recording of Adverse Events

12.4.1. Collection Period

Adverse events will be collected and recorded in EDC from Visit 1 (Day 0), until a participant completes study participation or until 30 days after he/she prematurely withdraws or is withdrawn from the study (without withdrawing consent). Serious Adverse Events, as defined in Section 12.2.4 *Serious Adverse Events*, Suspected Adverse Reactions, as defined in Section 12.2.2, *Suspected Adverse Reactions*, and adverse events related to study procedures will be collected and recorded in EDC from the time of consent until a participant completes study participation or until 30 days after he/she prematurely withdraws or is withdrawn from the study (without withdrawing consent).

12.4.2. Collecting Adverse Events

Adverse events (including SAEs) may be discovered through any of these methods:

- Observing the participant.
- Interviewing the participant [e.g., using a checklist, structured questioning, diary, etc.].
- Receiving an unsolicited complaint from the participant.

In addition, an abnormal value or result from a clinical or laboratory evaluation can also indicate an adverse event, as defined in Section 12.3, *Grading and Attribution of Adverse Events*.

12.4.3. Recording Adverse Events

Throughout the study, the investigator will record all adverse events and SAEs as described previously (Section 12.2, *Definitions*) on the appropriate AE/SAE eCRF regardless of the relationship to study therapy regimen or study procedure.

Once recorded, an AE/SAE will be followed until it resolves with or without sequelae, or until the end of study participation, or until 30 days after the participant prematurely withdraws or is withdrawn from the study, whichever occurs first (without withdrawing consent).

12.5. Reporting of Serious Adverse Events and Adverse Events

12.5.1. Reporting of Adverse Events

This section describes the responsibilities of the site investigator to report AEs to the study sponsor via the DAIT-SACCC (Division of Allergy, Immunology, and Transplantation Statistical and Clinical Coordinating Center).

Timely reporting of AEs of NCI-CTCAE Grade 2 and higher and Grade 1 or higher COVID-19 event is required. Unless otherwise noted below in Section 12.5.2 for SAEs, AEs must be recorded on the AE/SAE eCRF within five (5) days of discovery of the event. Whenever possible, a diagnosis should be provided, rather than compilation of signs/symptoms, with grade of the event dictated by highest grade of the sign/symptom component.

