12.5.2. Reporting of Serious Adverse Events to DAIT/NIAID (Sponsor)

This section describes the responsibilities of the site investigator to report SAEs to the Study Sponsor (NIAID/DAIT) via the AE/SAE eCRF. Timely reporting of adverse events is required by 21 CFR and ICH E6 guidelines.

When a site investigator identifies a SAEs, he or she must notify DAIT/NIAID via the DAIT-SACCC within 24 hours regardless of the relationship or expectedness. Site investigators are to report these events on the SAE eCRF in Electronic Data Capture (EDC). Should EDC become unavailable/ inaccessible, the site investigator should notify DAIT/NIAID via the DAIT-SACCC email at [contact]. This email can serve as the initial notification; however, within the next business day the SAE eCRF must be completed.

All requested information on the SAE eCRF should be provided. Unavailable details of the event at time of initial report should not delay submission of known information. The initial report should include at a minimum: AE term, relationship to tofacitinib, and reason why event is serious (per definitions). Supplementary Case Report Form (CRF) pages including medical history, concomitant medications, demographics, study drug administration, and death must be provided. As additional details become available, the SAE eCRF should be updated and submitted. With each iteration of the form, the investigator (or designated sub-investigator) must sign the form electronically.

For additional information regarding SAE reporting, contact Rho Product Safety (DAIT-SACCC):

Rho Product Safety

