12.8. Review of Safety Information

12.8.1. Medical Monitor Review

The DAIT/NIAID Medical Monitor shall receive monthly reports from the DAIT-SACCC compiling new and accumulating information on AEs, SAEs, and pregnancies recorded by the study site on appropriate eCRFs.

In addition, the Medical Monitor shall review and make decisions on the disposition of the SAE and pregnancy reports received by the DAIT-SACCC (See Sections 12.5.1, *Reporting of Serious Adverse Events to DAIT/NIAID*, and 12.6, *Pregnancy Reporting*).

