12.8.2.2. Ad hoc DSMB Reviews

In addition to the pre-scheduled data reviews and planned safety monitoring, the DSMB may be called upon for *ad hoc* reviews. The DSMB will review any event that potentially impacts safety at the request of the protocol chair or DAIT/NIAID. In addition, the following events will trigger an *ad hoc* comprehensive DSMB Safety Review:

- Any death considered possibly or definitely related to study treatment or procedures.
- The occurrence in 2 participants of Grade 3 or higher AEs or SAEs with the same MedDRA preferred terms considered at least possibly related to study treatment or procedures.
- The occurrence in 2 participants of Grade 3 or higher infections.
- Any grade 2 or higher thromboembolic event.

After review of the data, the DSMB will make recommendations regarding study conduct and/or continuation.

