12.8.2.2.1. Temporary Suspension of Tofacitinib Dosing for ad hoc DSMB Safety Review

If a triggering event occurs and an ad hoc DSMB Safety Review is required (Section 12.8.2.2, *Ad hoc DSMB Reviews*), then a temporary halt in initiating dosage for new enrollees will be implemented. Participants on study treatment will continue as planned. If two weeks has elapsed and the ad-hoc DSMB has not met, then no new participants will be consented or enrolled until after the DSMB completes review of the safety data.

13. Statistical Considerations and Analytical Plan

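### Three of the four ad hoc DSMB triggers can be met by non-serious events, but these have no expedited route, no stated time limit and no named role for recognising them

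*Combined protocol and SAP*

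**What the plan says.** **Triggers.** Section 12.8.2.2 (repeated in the synopsis) lists four triggers. One is a related death. The other three are defined by grade: "Any grade 2 or higher thromboembolic event"; Grade 3 or higher infections in 2 participants; and Grade 3 or higher AEs or SAEs sharing a MedDRA preferred term in 2 participants and at least possibly related. The last names AEs alongside SAEs, so non-serious events are expressly included.

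**Consequence of a trigger.** Under Section 12.8.2.2.1, if a triggering event occurs, "then a temporary halt in initiating dosage for new enrollees will be implemented". Participants already on drug carry on. If the DSMB has not met within two weeks, consent and enrolment also stop until its review is complete.

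**Reporting.** For an SAE, Section 12.5.2 says that the site investigator "must notify DAIT/NIAID via the DAIT-SACCC within 24 hours regardless of the relationship or expectedness". For every other reportable AE, Section 12.5.1 says that "AEs must be recorded on the AE/SAE eCRF within five (5) days of discovery of the event".

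**Review.** Section 12.8.1: "The DAIT/NIAID Medical Monitor shall receive monthly reports from the DAIT-SACCC compiling new and accumulating information on AEs, SAEs, and pregnancies". Beyond that compilation, "the Medical Monitor shall review and make decisions on the disposition of the SAE and pregnancy reports received by the DAIT-SACCC"; non-serious AEs are not part of that individual review. Planned DSMB reviews are at least yearly (12.8.2.1).

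**The concern.** The triggers are written in terms of grade, while the reporting speed is written in terms of seriousness. An event can therefore count toward a mandatory DSMB review and still travel by the slow route. A Grade 2 thromboembolic event, or a Grade 3 infection or laboratory abnormality, that meets no seriousness criterion is in this position. Section 12.2.4 (item 6) allows an important medical event to be called serious, but that is a matter of judgment, so a mandatory trigger can depend on a discretionary label.

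Two of the three grade-based triggers also need events in two participants. With 1 to 3 sites, the two events may occur at different sites, and the protocol gives nobody the task of keeping the count.

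What is at stake is the halt on starting new participants. It can act only once somebody recognises that a trigger has been met. The protocol has no pre-specified stopping rules (11.5), and thrombosis and serious infection are both listed drug risks (5.1), so timely recognition matters.

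**Working it through.** **Inputs from the protocol**
- Entry of a non-serious AE: up to 5 days from discovery (12.5.1).
- SAE notification: 24 hours, taken as 1 day (12.5.2).
- Medical Monitor report: monthly, taken as 28 to 31 days (12.8.1).
- Dosing: Day 2 to Day 26 (8.5.1).
- Participants: 10 planned (3.1), with up to 3 + 18 = 21 replacements (11.3).
- Study duration: estimated at 1 year (synopsis).

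**Plan's own figure.** 26 − 2 + 1 = 25 daily doses, which reproduces the stated 25-day course.

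**Maximum lag to the Medical Monitor.** Longest entry time plus longest wait for the next report:
- 28-day month: 5 + 28 = 33 days.
- 31-day month: 5 + 31 = 36 days.

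This is 8 to 11 days longer than the course, against 1 day from identification to sponsor notification on the SAE route. Adding the two intervals is an inference: the protocol states each one but does not say that recognition of a trigger waits for the monthly report.

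**Mean lag (assumption: the report date is evenly spread relative to entry).**
- Entry evenly spread over 0 to 5 days: 2.5 + 28/2 = 16.5 to 2.5 + 31/2 = 18.0 days.
- Entry always on day 5: 5 + 28/2 = 19.0 to 5 + 31/2 = 20.5 days.

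The mean is therefore about 17 to 21 days. A simulation under the same assumptions gave the same means and put about 20% to 35% of events above 25 days. A lag longer than the course is the upper part of the range, not the typical case.

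**New participants starting in the gap (assumption: starts evenly spread over 365 days).**

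| Starts in the year | Lag | Calculation | New starts |
|---|---|---|---|
| 10 | mean, 17 to 21 days | 10/365 × 17 to 10/365 × 21 | 0.47 to 0.58 |
| 10 | maximum, 33 to 36 days | 10/365 × 33 to 10/365 × 36 | 0.90 to 0.99 |
| 31 (10 + 21) | maximum, 33 to 36 days | 31/365 × 33 to 31/365 × 36 | 2.80 to 3.06 |

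**Check for another route.** Section 12.8.2.2 lets the protocol chair or DAIT/NIAID ask for a DSMB review, but it gives no time limit and presupposes that they know of the event. No other section gives a non-serious trigger event an expedited path, a deadline for recognition, or a responsible role.

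**The case against.** The strongest reply is that the 33 to 36 days comes from silence in the text. Section 12.5.1 treats eCRF entry as reporting to the sponsor through the coordinating center, so the sponsor's agent holds the event by day 5 and could spot a trigger then. Section 15 adds that each page reaches the database when completed and that queries are handled on an ongoing basis. This stands in part. A reader might infer that the sponsor itself may not learn of the event for 36 days, and the documents do not support that. They support up to 5 days to the coordinating center, then no stated limit, with the monthly report as the only stated route to the Medical Monitor. That the center could notice earlier is true, but nothing requires it.

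Three further inferences are tempting and also go too far.
- **No single site could recognise a trigger.** The study may run at one site, two events may fall at the same site, and the thromboembolic trigger needs only one event. The gap in counting concerns pairs that span sites.
- **The ad hoc review and halt are the only study-level protection.** Reviews on request (12.8.2.2), DSMB reviews at least yearly (12.8.2.1) and timely reporting to IRBs (12.5.4) also exist.
- **Participants who finish their course during the gap are harmed by it.** Under 12.8.2.2.1 those already on drug continue after a trigger in any case, so faster recognition would not change their dosing.

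The affected participant is covered by individual rules: permanent discontinuation after a Grade 2 or higher thromboembolic event (6.5.1) and suspension for a Grade 2 or higher infection (6.5.2). Those rules do not reach the next person to be started, whom the halt is meant to protect.

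It is also fair that many trigger events would be serious and so use the 24-hour route. How many would not is unknown. Coordinating-center and DSMB procedures are not among the documents, so actual practice cannot be judged.

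**Conclusion.** The gap is real but bounded. Three of the four triggers can be met by events that may take up to 5 days to reach the coordinating center instead of 24 hours. From there the protocol sets no deadline and names no role for recognising a trigger.

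The exposure is about 0.5 to 1 new participant starting dosing before the Medical Monitor's report at planned accrual. It rises to about 3 only if the lag is at its maximum and all 21 replacements are enrolled within the same year. These figures assume evenly spaced starts and reports, and that recognition comes through the monthly report; earlier recognition at the coordinating center would reduce them. The related-death trigger, and any trigger event that is also an SAE, is unaffected.

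The point is worth acting on because a faster route already exists in the protocol and extending it is cheap. It does not show that participants already on drug are left unprotected.

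**What to change.** In Sections 12.5.1 and 12.5.2, require any event that could count toward a Section 12.8.2.2 trigger to be notified within 24 hours by the existing SAE route, whether or not it is serious. That covers Grade 2 or higher thromboembolic events, Grade 3 or higher infections, and Grade 3 or higher AEs at least possibly related to study treatment or procedures.

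In Section 12.8.1, have the coordinating center forward these reports to the Medical Monitor on receipt and keep the trigger count across sites.

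A lighter option is one sentence naming who checks incoming AEs against Section 12.8.2.2 and within what time. It would fill the silence but leave the 5-day entry allowance in place.

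The cost is a few lines of amendment text and a few additional expedited reports in a 10-participant study. No visit, assessment, dose or clinical rule changes.
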